### **Inclusion/Exclusion Criteria**

The following criteria are required for study inclusion: 1) age 18 to 29 years; 2) identifies as male; 3) identifies as gay/bisexual or reports having sex with men in past 12 months; 4) identifies as Latino/Hispanic; 5) self-reports being HIV-uninfected; 6) resides in San Diego County, California; 7) speaks English or Spanish; 8) is willing and able to provide informed consent; and 9) reports at least one HIV risk factor as informed by Centers for Disease Control and Prevention (CDC) guidelines. MSM are at elevated risk for HIV if they report one of the following: 1) an HIV-positive sexual partner; 2) diagnosis of a bacterial sexually transmitted infection (STI) within the past 12 months; 3) engaging in

condomless anal sex with a non-monogamous partner in the past 12 months; 4) engaging in commercial sex work in the past 12 months; 5) injection of illicit drugs and sharing of injection equipment in the past 12 months; or 6) engaging in drug treatment for injection drug use in the past 12 months. Individuals will be excluded if they self-report being HIV-positive. The intervention is designed to meet the needs of MSM who self-report their gender identity as male, but other gender identities are allowed in the study. If a potential participant indicates that their gender identity is not “male” (e.g., transgender, non-binary, gender fluid), then the participant will be informed that the study was designed for cis-male MSM; and will then be invited to determine whether they feel that they will benefit from the study based on their gender identity. Participants who previously were prescribed or are currently taking PrEP will be included in the study. Participants are not required to seek care at FHCSO to be included in the study.

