### **Recruitment**

Non-probability (convenience) sampling will be used to recruit participants within the greater San Diego area via a variety of methods, including through FHCSO outreach and HIV/STI testing programs, a Spanish language Latino MSM support group, gay-friendly events, such as Pride, and flyering local LGBT community centers, gay-identified/friendly coffee shops, gyms, and bars. We will also utilize online recruitment methods, including targeted ads through Facebook and Instagram, and use of geolocation social networking mobile applications tailored to sexual minority men (e.g., Grindr, Scruff, Jack’d). Potential participants recruited using flyering or targeted ads will be requested to contact study personnel via email or telephone. A bilingual member of the study team will contact each potential participant via telephone to explain the study and screen for inclusion. The bilingual research assistants will be native Spanish speakers who are bilingual in English and Spanish; they will have some university education and research experience. If a potential participant screens positively for the study, an in-person baseline visit will be scheduled, in which the inclusion/exclusion criteria will be assessed in further detail. Reasons for non-participation of potential participants will be documented.

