Sexual Behaviors	3 items measuring over the past 3 months the total number of male anal sex partners, number of partners in which condoms were not used exclusively, and the HIV status of partners. Data are collected using numeric text entries.		X	X	X	
Mental health	21 item Depression, Anxiety, Stress Scale (DASS-21) measuring depression, anxiety, and stress over the past week. Data are collected using a Likert scale.	Lovibond & Lovibond, 1995	X	X	X	
Substance use	15 items measuring drug, alcohol, and tobacco use over the past month. Data are collected using a Likert scale.	Team developed	X	X	X	
Social support	8-item PROMIS Informational and 7-item Emotional Support Scales, respectively, measuring perceived sources of support over the past month. Data are collected using a Likert scale.	Hahn et al., 2014	X	X	X	
Patient Satisfaction with PrEP-related services	8-item Client Satisfaction Questionnaire (CSQ-8) measuring of satisfaction with PrEP-related health care services received. Data are collected using a Likert scale.	Attkisson & Greenfield, 2004		X	X	
Satisfaction with Interpersonal	For participants randomized to PN intervention only; 9-item measure of satisfaction with care provided by a patient navigator. Data are collected using a Likert scale.	Jean-Pierre et al., 2012		X	X	

Relationship with Navigator						
PN Intervention Acceptability	For participants randomized to PN, brief telephone key informant interview assessing acceptability of the PN intervention. Data are qualitative.	Team developed			X	
PrEP Initiation	Up to 10 survey items assessing whether patient had received a prescription for PrEP, decided to fill a PrEP prescription, and taken at least one dose of PrEP since the start of the study. Categorical data are collected.	Team developed	X	X	X	
Demographic Characteristics	Demographic items (e.g., age, race, gender, sexual orientation, relationship status, country of origin, U.S. citizen status, primary language, education level, employment status, income, health insurance status) have categorical response options. Age data are collected with numeric text entry.		X			
Medical Characteristics	Comorbid medical conditions, medications prescribed, history of STI testing					X

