PrEP-Related Health Care Received	Date(s) appointment scheduled for PrEP consultation; Date attended appointment for PrEP consultation; Date(s) health care provider wrote PrEP prescription(s); Date the first follow-up PrEP appointment(s) scheduled; Date(s) of follow-up medical appointment attended; Data recorded in EHR regarding adherence and discontinuation; other data regarding PrEP-related health care	Team developed				X

Abbreviations: BL = baseline; 3m = 3 month follow/up appointment; 6m = 6 month follow-up appointment; EHR = electronic health record; STI= sexually transmitted infection; PN = patient navigation

**MEMS Device Data Collection.** At baseline and 3-month follow-up, all participants will be asked if they have obtained a prescription for PrEP. Those who indicate that they have been prescribed PrEP and have taken at least one pill will be asked to track their PrEP adherence via a Medication Event Monitoring System (MEMS) device. A MEMS device is a standard prescription bottle that includes a larger lid containing a MEMS monitoring cap. During the baseline or at a 3-month follow-up visit, the research coordinator will give participants a MEMS device with instructions for its use. Participants will be instructed to place all PrEP pills into a MEMS container so when a pill is removed, the device will record date and time of removal of the medication dose using a small microcircuit. A medication “event” is removal of bottle closure, followed by replacement of closure. A study staff member will collect MEMS devices from participants in-person at the 3- and/or 6- month follow-up and connect them to a MEMS® Reader, which transfers data to a secured server via a secured web platform. Timing adherence will be calculated as percentage of time each participant took PrEP as prescribed by determining number of doses of PrEP taken at 24-hour intervals for a once daily PrEP regimen and dividing it by number of days adherence was monitored with MEMS.

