**Medical Record Data Collection.** We will collect the following data from electronic health records (EHRs) 6 months following study enrollment after obtaining a written release of information: 1) date(s) initial appointment to speak to a health care provider regarding PrEP was scheduled; 2) date participant attended an initial appointment to discuss PrEP; 3) dates and number of prescriptions written for PrEP by a health care provider; 4) date the first follow-up visit related to PrEP was scheduled; and 5) dates the participant attended follow-up appointments related to PrEP. We will document EHR data regarding PrEP initiation and adherence, barriers to PrEP adherence, exams and laboratory tests required to obtain an initial or follow-up PrEP

prescription, side effects attributed to PrEP, diagnosis and treatment of illness during the study, prescription medications, comorbid health conditions, and history of STI testing. We will also note whether the EHR indicates that participants decided to cease taking PrEP and the date of discontinuation.

**PN Intervention Encounter Data.** Using an approach developed by the Patient Navigation Research Program (PNRP), patient navigators will record process data related to the PN services provided, including: 1) number of encounters; 2) length of time of each encounter; 3) barriers experienced by patients; and 4) actions taken to reduce barriers. The patient navigators will also be asked to keep detailed qualitative notes regarding telephone, text, and in-person encounters with participants, including participants' progress in the PrEP continuum, successes in implementing the PN intervention, and challenges in implementing the PN intervention.

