To test the preliminary impact of the intervention, a series of logistic regression models will be conducted, with each of the 6 binary PrEP continuum primary outcome variables set as a criterion: 1) appointment scheduled for PrEP consultation; 2) appointment attended for PrEP consultation; 3) PrEP prescription received; 4) PrEP prescription filled; 5) PrEP initiated; and 6) PrEP follow-up medical appointment attended. In addition, we hypothesize that receipt of the PN intervention will be associated with increased self-reported PrEP adherence over the past seven days (also a primary outcome variable). To test the preliminary impact on the two measures of self-reported PrEP adherence, we will conduct two linear regression analyses with intervention group assignment entered as the independent variable and each measure of PrEP adherence entered as the dependent variable. Potential demographic variables (e.g., age) will be assessed for inclusion in the models as well. Finally, linear mixed models will be conducted to examine changes in 1) barriers to PrEP-related care; 2) PrEP knowledge, 3) PrEP efficacy beliefs; 4) medication beliefs, 5) PrEP attitudes; and 6) medication self-efficacy. Linear mixed models allow us to account for the dependence of the repeated measures. Different covariance structures will be implemented and the information criterion such as AIC or BIC will be used for model selection. We hypothesize that participants randomized to PN will have greater engagement in PrEP continuum behaviors compared to participants randomized to UC. Since data analyses are exploratory, and there is not adequate statistical power to evaluate efficacy of the PN intervention, these tests can only provide information regarding data trends and effect sizes. If the study and PN intervention methods are found to be feasible and acceptable, a larger study with adequate statistical power will be conducted to appropriately evaluate the efficacy of the PN intervention.

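### Two primary appointment outcomes rest on the initial PrEP visit, with no date window and no scoring rule for the prior PrEP users the trial enrols

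*Combined protocol and SAP*

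**What the plan says.** **Eligibility** (Inclusion/Exclusion Criteria): "Participants who previously were prescribed or are currently taking PrEP will be included in the study". No cap is set on their number.

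**Chart abstraction** (Medical Record Data Collection): "We will collect the following data from electronic health records (EHRs) 6 months following study enrollment". The first item is the "date(s) initial appointment to speak to a health care provider regarding PrEP was scheduled"; the second is "2) date participant attended an initial appointment to discuss PrEP". The six months says when the chart is read. It does not say how far back an event may lie. The only limit to the study period in that paragraph is attached to illness.

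**Table 1**, row on PrEP-related health care, lists "Date(s) appointment scheduled for PrEP consultation; Date attended appointment for PrEP consultation". It is marked for the 6-month chart review only. The word *initial* is absent, and so is any window.

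**SAP**, quantitative data: the first two of the six binary primary outcomes are "1) appointment scheduled for PrEP consultation; 2) appointment attended for PrEP consultation". Again there is no *initial*, no window and no rule for prior users. The only covariates mentioned for these models are demographic. Randomization uses blocks of 4 with no stratification by PrEP history stated, and the analysis is by intention to treat, so prior users stay in.

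**Contrast**: the PrEP Initiation survey row in Table 1 is anchored in time ("taken at least one dose of PrEP since the start of the study"). That survey covers prescription, fill and first dose, not the consultation.

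**The concern.** A former or current PrEP user will normally have had a first PrEP consultation before enrolment. The only detailed collection rule for the two appointment outcomes points the abstractor at that visit. An outcome settled before randomization cannot respond to the arm.

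The SAP disclaims power and says the tests inform on trends and effect sizes, in preparation for a larger trial. Effect sizes are therefore a main quantitative product of this pilot. For two of its seven primary outcomes they would be diluted by an amount that depends on how many prior users happen to enrol.

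**Working it through.** The plan gives no power calculation, effect size or event rate for these outcomes, so there is no stated figure to reproduce. The check is a reading of the text, followed by an illustration on assumed rates.

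**1. How a former user is scored.** Take someone who stopped PrEP before the study and attends a restart visit after randomization.

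| Rule applied | Score | Can it respond to arm? |
|---|---|---|
| Initial visit, any date (Medical Record Data Collection, literal) | yes, from the old visit | no |
| Initial visit, later dates only | no, the restart is not initial | no |
| Any consultation, any date (Table 1 and SAP, literal) | yes, from the old visit | no |
| Any consultation dated after randomization | yes, from the restart | yes |

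Only the last row works, and no section states it. Adding a start date alone moves the plan from row 1 to row 2.

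**2. Dilution of the risk difference.** Let p_C and p_T be the usual-care and navigation rates among people with no earlier visit. Let f be the share of prior users, equal in both arms, each with the old visit visible in the chart.

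- Scored yes: the arm rates are f + (1 − f)p_C and f + (1 − f)p_T.
- Scored no: the arm rates are (1 − f)p_C and (1 − f)p_T.
- Either way the difference is (1 − f)(p_T − p_C).

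Assume 30% and 60%. At f = 20%, scored yes: 0.2 + 0.8 × 0.3 = 0.44 and 0.2 + 0.8 × 0.6 = 0.68. The difference is 24 points, and the odds ratio is (0.68/0.32)/(0.44/0.56) = 2.70. Scored no: 0.24 and 0.48, again 24 points, with odds ratio (0.48/0.52)/(0.24/0.76) = 2.92.

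| f (assumed) | Risk difference | Odds ratio, scored yes | Odds ratio, scored no |
|---|---|---|---|
| 0 | 30 points | 3.50 | 3.50 |
| 10% | 27 | 3.03 | 3.17 |
| 20% | 24 | 2.70 | 2.92 |
| 30% | 21 | 2.47 | 2.72 |

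The differences are the same for assumed rates of 20% and 50%, or 40% and 70%. Odds ratios are shown because the SAP plans logistic regression.

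**3. Chance imbalance.** Assume 30 per arm (60 participants, equal allocation). The hypergeometric probability that the arms differ by 4 or more prior users is 20% with 6 prior users in all, 33% with 12 and 40% with 18.

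Take 12 prior users, scored yes, with the same 30% and 60%:

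- 8 in navigation and 4 in usual care: (8 + 22 × 0.6)/30 − (4 + 26 × 0.3)/30 = 0.707 − 0.393 = 31 points.
- The reverse split: (4 + 26 × 0.6)/30 − (8 + 22 × 0.3)/30 = 0.653 − 0.487 = 17 points.

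A gap of 4 people thus moves the estimate about 7 points either way around the expected 24.

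**The case against.** The strongest reply is that the outcomes themselves are not defined by the initial visit. Table 1 and the SAP omit the word. In the abstraction list it may serve only to separate a consultation from the follow-up visits listed after it. On that reading a return consultation can count. This stands, and it defeats the inference that prior users' values are fixed on every reading of the documents. It does not settle the matter, because the same texts have no window and an old consultation would satisfy them too.

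Second, the abstraction records dates, so an analyst could apply a post-randomization rule later. This largely stands and makes the remedy cheap. But the rule is unwritten, and it should not be chosen after the data are seen. Table 1 also provides for one attendance date only, so a restart visit after an old one is not assured a place, except perhaps among the follow-up visits.

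Third, a reader might infer that bringing lapsed users back to care cannot show in this trial. The documents do not support that. A restart can appear in prescription received, prescription filled, initiation, adherence and follow-up attendance, and the survey is anchored to study start.

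Fourth, a reader might infer that many participants arrive with a consultation already booked, because recruitment runs "including through FHCSO outreach and HIV/STI testing programs". The Recruitment section says nothing about bookings and lists many other channels.

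Fifth, the pull toward no effect holds only in expectation, as the imbalance example shows. If prior users are scored no in both arms, the risk ratio does not change (0.48/0.24 = 0.60/0.30 = 2).

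**Conclusion.** The concern holds in this limited form. The plan admits prior PrEP users, its one detailed collection rule directs the abstractor to the wrong visit for them, and nothing in Table 1 or the SAP supplies a window or a scoring rule. Two of the six binary primary outcomes are affected.

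The expected risk difference is multiplied by (1 − f). This rests on equal f in both arms and on the earlier visit being identified. The share f and the event rates are not in the documents, so every point value above is an illustration; only the direction in expectation follows from the text.

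The analyses are declared exploratory and no efficacy claim depends on them, which limits the seriousness. It is more than a wording slip, because a start date alone would leave prior users fixed at no.

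**What to change.** In Table 1 (PrEP-related health care row), Medical Record Data Collection and the SAP:

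- Define the two outcomes as any PrEP consultation, first or restart, that was scheduled, or attended, on a date after randomization and up to 6 months.
- Abstract earlier PrEP appointments and bookings as a separate baseline field.
- Report both outcomes by baseline PrEP status (never, former, current). Under the new definition, current users and people already booked can still contribute little to these outcomes, and pooled results alone would hide that.

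The baseline survey can supply the status: everyone is asked at baseline about a PrEP prescription, and the initiation and 7-day adherence items are given then. The baseline wording should be checked, since Table 1 describes the initiation items relative to study start.

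The cost is wording in the abstraction form and the SAP, with no new visits or contacts. The abstractor will have to classify some restart visits, and with 60 participants the status groups will be small and suited to description only.

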### **Monitoring**

Consistent with NIMH requirements, a data monitoring committee is not required given this is not a phase III clinical trial and because of the low-risk nature of this exploratory study.

## Statistical Analysis Plan

**Qualitative data.** Qualitative data (key informant interviews, navigator qualitative notes, supervisor notes) will be saved in a text file to import into NVivo for analysis. The study PIs will review the qualitative data using a content analysis technique, which identifies emergent themes occurring during discussion. Code mapping will be used to develop a preliminary set of codes (themes) corresponding to each potential strength of the PN intervention as well as every potential aspect for improvement. Then, the co-PIs will independently code the remaining data and meet to discuss and achieve consensus in coding. Once coded, the data will be summarized by theme. These data will be used to modify the PN intervention, if necessary, or will provide further indication that the PN intervention should be tested in a larger scale study.

**Quantitative data.** All quantitative data will be summarized descriptively to determine aspects of the PN intervention that worked well and potential areas of improvement of the PN intervention. Our biostatistician will be blinded to intervention assignment for participants and will conduct statistical analyses using SAS 9.4. Univariate statistics will be conducted for outcomes measured at baseline and 6-month follow-up to describe sample characteristics between the two groups (UC versus PN). Attrition in the two groups will be compared. Characteristics of individuals with missing values and individuals with no missing values will be studied. Multiple imputation technique will be implemented and sensitivity analysis will be conducted to assess if missing data is at random. Assumptions of statistical tests will be evaluated. For assessing preliminary impact, the primary outcomes are seven behaviors associated with the PrEP care continuum (i.e., appointment scheduled for PrEP consultation; appointment attended for PrEP consultation; PrEP prescription received; PrEP prescription filled; PrEP initiated; self-reported PrEP adherence over the past seven days; and PrEP follow-up medical appointment attended).

To test the preliminary impact of the intervention, a series of logistic regression models will be conducted, with each of the 6 binary PrEP continuum primary outcome variables set as a criterion: 1) appointment scheduled for PrEP consultation; 2) appointment attended for PrEP consultation; 3) PrEP prescription received; 4) PrEP prescription filled; 5) PrEP initiated; and 6) PrEP follow-up medical appointment attended. In addition, we hypothesize that receipt of the PN intervention will be associated with increased self-reported PrEP adherence over the past seven days (also a primary outcome variable). To test the preliminary impact on the two measures of self-reported PrEP adherence, we will conduct two linear regression analyses with intervention group assignment entered as the independent variable and each measure of PrEP adherence entered as the dependent variable. Potential demographic variables (e.g., age) will be assessed for inclusion in the models as well. Finally, linear mixed models will be conducted to examine changes in 1) barriers to PrEP-related care; 2) PrEP knowledge, 3) PrEP efficacy beliefs; 4) medication beliefs, 5) PrEP attitudes; and 6) medication self-efficacy. Linear mixed models allow us to account for the dependence of the repeated measures. Different covariance structures will be implemented and the information criterion such as AIC or BIC will be used for model selection. We hypothesize that participants randomized to PN will have greater engagement in PrEP continuum behaviors compared to participants randomized to UC. Since data analyses are exploratory, and there is not adequate statistical power to evaluate efficacy of the PN intervention, these tests can only provide information regarding data trends and effect sizes. If the study and PN intervention methods are found to be feasible and acceptable, a larger study with adequate statistical power will be conducted to appropriately evaluate the efficacy of the PN intervention.

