Developing a Patient Navigation Intervention for PrEP Continuum of Care Among Young Latino MSM  
(PrEParate)  
Study Protocol and Statistical Analysis Plan  
NCT04048382  
August 2, 2019

Using a randomized controlled trial design, a pilot test of the PN intervention will be conducted in collaboration with the Family Health Centers of San Diego (FHCS), a federally qualified health center. Bilingual research assistants will recruit 60 young adult Latino MSM at-risk for HIV in San Diego County, California; this sample size is well within the bounds of recommendations for pilot trials. After a research assistant obtains informed consent, participants will complete baseline surveys, and then the research assistant will individually randomize each participant to 1 of 2 conditions: usual care plus written information (UC) or PN. At 3- and 6-month follow-up, participants will be asked to complete surveys. Individuals randomized to PN will also be asked to participate in a key informant interview at 6-months. Participants' electronic health records (EHR) will be reviewed at 6-month follow-up to assess their engagement in the PrEP continuum. The study methods and PN intervention will be reviewed for feasibility and acceptability, as well as preliminary impact of the PN intervention in preparation for a future full-scale efficacy trial. In addition, the pilot test will evaluate preliminary impact on seven PrEP continuum-related primary outcomes (i.e., scheduled and attended PrEP consultation; PrEP prescription received; PrEP prescription filled; PrEP initiated; self-reported PrEP adherence; and PrEP follow-up medical appointment attended). Analyses will be performed under the intent-to-treat (ITT) principle. Participants will be compensated with a \$50 gift card to an online retailer at each of the three assessment time points (baseline, 3-month follow-up, 6-month follow-up). (See Appendices 1-3 for informed consents and WHO Trial Registration Data Set)

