### **Randomization**

The research coordinator will use the Randomizer for Clinical Trial computer application to randomize each participant to either UC or PN via an iPad immediately following the baseline survey data collection. Randomizer for Clinical Trial will implement a blocked randomization sequence (in blocks of 4 participants) to balance randomization across the arms of the study. The randomization sequence will be concealed from all members of the study team prior to randomization.

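### The six logistic models have no small-sample estimator: with about 30 per arm, a Firth penalty and a reported risk difference would be a cheap improvement, mainly for the late care steps

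*Combined protocol and SAP*

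**What the plan says.** The opening paragraph of the protocol sets the size: "Bilingual research assistants will recruit 60 young adult Latino MSM at-risk for HIV in San Diego County, California". It gives no power calculation, only the remark that "this sample size is well within the bounds of recommendations for pilot trials". The Randomization section assigns participants to two arms "in blocks of 4 participants) to balance randomization across the arms of the study".

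The Statistical Analysis Plan (quantitative data) then says that "a series of logistic regression models will be conducted", "with each of the 6 binary PrEP continuum primary outcome variables set as a criterion". The outcomes follow the care pathway: consultation scheduled, consultation attended, prescription received, prescription filled, PrEP started, follow-up visit attended. Demographic covariates may be added, but their number is not fixed. The biostatistician "will conduct statistical analyses using SAS 9.4". Missing data are to be multiply imputed.

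The plan concedes that power is inadequate for efficacy and that "these tests can only provide information regarding data trends and effect sizes". It names no estimator beyond logistic regression, no rule for empty cells, no risk difference and no confidence interval. It promises in general terms to evaluate test assumptions and to summarise the quantitative data descriptively.

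**The concern.** If each step depends on the one before, the last steps have the fewest events. When one arm has none and the other has some, the maximum-likelihood odds ratio is infinite or zero and its Wald interval has no meaning. With one or two events the estimate is finite but can move greatly when a single participant changes category. Adding covariates to 60 records makes both problems somewhat worse, and an infinite estimate in any imputed data set cannot be pooled.

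By the plan's own account, trends and effect sizes are all that these tests can offer, and preliminary impact is assessed in preparation for a full-scale trial. An odds ratio that is undefined or far from the truth serves that use poorly. If the remedy is chosen only after an empty cell appears, the choice is post hoc.

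**Working it through.** **Inputs.** From the documents: 60 participants, two arms, blocks of 4, six binary outcomes, SAS 9.4. Inferred: 60/4 = 15 full blocks, hence 30 per arm if each block splits 2:2. Assumed, because the documents give no figure: usual-care (UC) and navigation (PN) event rates, shown as a range; and 20% missing data, giving 24 per arm, as a second case. The plan's 60 has no formula behind it, so there is no figure of its own to reproduce.

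**Step 1: chance of no usual-care event**, (1 − p)^n.

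- 30 per arm: 0.95^30 = 21%, 0.90^30 = 4%, 0.80^30 = 0.1%.
- 24 per arm: 0.95^24 = 29%, 0.90^24 = 8%, 0.80^24 = 0.5%.

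**Step 2: how often each estimator is wrong by a factor of two.** Let x of n usual-care and y of n navigation participants have the event. In the unadjusted model:

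- Maximum likelihood (ML): OR = y(n − x) / [(n − y)x].
- Firth: OR = (y + 0.5)(n − x + 0.5) / [(n − y + 0.5)(x + 0.5)]. In a 2×2 table the penalty equals adding 0.5 to each cell.

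Every table was enumerated with its binomial probability at n = 30. A twofold error is an estimate above twice, or below half, the true odds ratio. An infinite estimate counts as too high and a zero estimate as too low. Both directions are counted, because the penalty pulls estimates down and a count of overestimates alone would flatter it.

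| UC vs PN rate | True OR | ML, twofold error | Firth, twofold error |
|---|---|---|---|
| 3% vs 20% | 8.08 | 61% | 51% |
| 5% vs 20% | 4.75 | 51% | 42% |
| 10% vs 30% | 3.86 | 38% | 31% |
| 20% vs 40% | 2.67 | 25% | 21% |
| 40% vs 60% | 2.25 | 19% | 16% |

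The difference is 10, 9, 7, 4 and 3 percentage points. At 24 per arm the same enumeration still favours Firth in the first four rows, but the two are equal at 40% vs 60% (24% each).

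**Step 3: where the error comes from.** At 10% vs 30%, ML is infinite or more than twice the truth in 23% of trials: 4% infinite and 19% finite. At 20% vs 40% the total is 15%, of which 0.1% is infinite. At 40% vs 60% it is 12%, none of it infinite. Above the lowest rates, most of the error is therefore ordinary sampling noise.

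**Step 4: bias of the Firth log odds ratio** at 30 per arm: about −0.2 at 3% vs 20%, −0.06 at 5% vs 20%, and near zero at usual-care rates of 10% or more.

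**Step 5: covariates.** In a simulation of 3,000 trials per scenario with two unrelated covariates, the geometric mean of the finite ML odds ratios was 4.30 against a true 3.86 (10% vs 30%), 2.95 against 2.67 (20% vs 40%) and 2.40 against 2.25 (40% vs 60%), that is 11%, 11% and 7% high. Firth gave 3.85, 2.68 and 2.26.

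**Step 6: two example tables.**

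- 1/30 vs 8/30: ML OR = (8 × 29)/(22 × 1) = 10.5, Wald 95% CI 1.2 to 90.7. Firth OR = (8.5 × 29.5)/(22.5 × 1.5) = 7.4. Risk difference = 7/30 = 0.23.
- 0/30 vs 6/30: ML OR is infinite. Firth OR = (6.5 × 30.5)/(24.5 × 0.5) = 16.2. Risk difference = 6/30 = 0.20.

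**The case against.** A reader might infer that the plan will return infinite odds ratios for its outcomes in general. The documents do not support that. No usual-care rate is given, and what they do say points away from 3% to 5%. The Inclusion/Exclusion Criteria admit past and current PrEP users. Table 1 counts prescriptions and doses since the start of the study, which continuing users can meet. The Usual Care Intervention section gives that arm PrEP information and access to care at little or no cost. This objection stands: separation is a matter for the late steps, if any, and at a usual-care rate of 20% it practically disappears.

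A reader might also infer that these odds ratios are the pilot's main product. They are one output. The plan makes the larger study depend on feasibility and acceptability, and nowhere says that the odds ratios will set its size.

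Third, maximum likelihood is not written down, and SAS 9.4 does not prevent another choice. That is true, but unqualified logistic regression is normally read that way, and evaluating assumptions names no remedy.

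Fourth, the penalty is no cure: it moves some overestimates to the other side, and most of the error is sampling noise that the plan already concedes. This also stands. But with errors in both directions counted, Firth is still better at every rate tried at 30 per arm.

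Finally, profile-penalised and score-type intervals do not pool directly by Rubin's rules, so the change is more than one keyword. The fix has to allow for that.

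**Conclusion.** The point holds as a cheap improvement of minor to moderate weight. The analysis is not invalid. With about 30 per arm, the method that the plan most naturally describes can give an infinite odds ratio for a late, rare step, and it misses the truth by a factor of two somewhat more often than a penalised fit: 3 to 10 percentage points more over the range examined. The gain is largest where events are rare and small where they are common.

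This rests on an inferred 1:1 split, on maximum likelihood as the reading of the plan, and on assumed event rates. Because the true rates are unknown, an estimator that is finite at all of them is the safer one to prespecify. Neither method makes the estimates precise: 0/30 vs 6/30 still gives an odds ratio near 16 under the penalty. For that reason the risk difference should stand beside it.

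**What to change.** State before analysis:

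- All six binary models are fitted with the FIRTH option in PROC LOGISTIC.
- For each outcome, the proportion per arm and the risk difference with a score-type 95% CI (Miettinen-Nurminen or Newcombe) are reported alongside the odds ratio.
- In the complete-data analysis, odds ratios carry profile-penalised 95% CIs.
- In the multiply imputed analysis, the Firth log odds ratios with their standard errors, and the risk differences with theirs, are pooled by Rubin's rules. These pooled intervals will not be of the profile or score type, and the report should say so.

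The cost is one model option, one table and a little pooling work. The statistical price is shrinkage of about −0.2 on the log odds ratio at 3% vs 20%, and almost none at usual-care rates of 10% or more.
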